Vaginal suppositories will be self-applied by the subjects in the evening right after going to bed. Subjects will be advised not to have sexual intercourse during the nights in which they applied vaginal suppositories and to perform a vaginal douche in the morning. Subjects will be instructed to suspend the application of vaginal suppositories during the first 3 days of their menses. Subjects will be advised to keep the study medication refrigerated. In case of persistent side effects in subjects of the imiquimod group, the dose of the study medication will be modified and participants will receive vaginal suppositories containing only 50% of the original imiquimod dose (vaginal suppositories containing 3.125 mg imiquimod).

Missed doses of imiquimod can be made up the following day. Otherwise, the dose must be skipped and subjects should take the next scheduled dose at the usual time.

Imiquimod will be dispensed in boxes containing 18 vaginal suppositories (treatment weeks 1-8) at the beginning of the treatment course. During follow up visit at week 8 (see below), subjects will be provided a new box of 24 vaginal suppositories to complete treatment course for weeks 9-16. Study drug will be prescribed by the investigator and may be dispensed either by the investigator or study staff.

HIC#: 1603017415 Protocol version 11.0

CIN 2/3

11

(3) Imiquimod + HPV vaccine: At the baseline visit, this group will be instructed about the correct method of self-application of imiquimod 6.25mg as a vaginal suppository as described above, storage of medication, possible side effects. Subjects will be provided a diary and case report form to record vaginal suppository application and side effects will be recorded per NCI Common Terminology Criteria for Adverse Events (CTCAE 4.0). In addition, all women (regardless of age) will be administered a dose of the HPV vaccine on day of enrollment (regardless of previous HPV vaccination history). Women previously unvaccinated will receive an additional booster dose at 8 weeks. Local pain will be assessed with a visual analog scale immediately after vaccine administration and 5 minutes later. Subjects will be provided a separate case report form to record vaccine side effects per CTCAE 4.0.

Missed doses of imiquimod can be made up the following day. Subjects are encouraged to complete taking all prescribed doses. If additional time is required toward this goal of treatment, the scheduled dosing period may be extended.

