7.1.1 Dose reduction for imiquimod

Treatment related toxicities will be managed by treatment interruptions and possible dose reductions of imiquimod according to the schedule described in the below Tables. Dose reductions will apply to individual subjects only. Once the dose has been reduced, it cannot be increased later.

To prevent the development of more severe adverse events, treatment related rash/skin irritation should be managed early and proactive as described in the below Tables. Table 1: Dose reduction scheme for imiquimod

HIC#: 1603017415 Protocol version 11.0

AE type and CTCAE Grade	Action	Dose reduction scheme
Figure 2 • Dermatologic or local inflammatory reactions which responds promptly to symptomatic treatment (e.g., antihistamines, NSAIDS, narcotics); prophylactic medications indicated for ≤ 24 hrs • Vulvar edema with readily apparent obscuration of anatomic architecture, obliteration of skin folds, deviation from normal anatomic contour • Any drug related AE Grade ≥3	Pause treatment until subject has recovered to Grade ≤1 or baseline¹. Resume treatment. May reduce dose according to schedule opposite. If subject has not recovered to Grade ≤1 or baseline¹ within 21 days study treatment must be permanently discontinued².	If subject was receiving 6.25 mg, resume treatment at a dose of 3.125. If subject was receiving 3.125 mg, discontinue imiquimod.

- 1 Baseline is defined as the CTCAE (version 4) Grade at the start of treatment
- In the event that the subject is deriving obvious clinical benefit according to the investigator's judgement, further treatment with imiquimod will be decided by the investigator.

In the event of any unrelated adverse events, the investigator may choose to interrupt the medication for up to 21 days, but no dose reduction should occur. If the medication is interrupted for more than 21 days, the decision to continue with imiquimod will be made by the investigator.

7.2 Management of adverse events, concomitant therapy, restrictions and rescue treatment

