7.2.2 Management of expected adverse events

Dermatologic and local inflammatory adverse events are the most common side-effects associated with treatment with imiquimod. Respiratory symptoms are less commonly reported but can include sinusitis, upper respiratory tract infection or flu-like symptoms. Treatment of these side-effects should be proactive and should be started as early as possible after onset of symptoms.

7.2.2.1 Management of dermatologic and local inflammatory adverse events following treatment with imiquimod

Dermatologic adverse events including localized erythema, xeroderma, crusted skin, erosion or ulceration, edema, vulvar pain or pruritus can occur after a few applications of imiquimod. Although usually mild to moderate, dermatologic reactions can cause significant discomfort (Table 7.2.2.1: 2).

Table 2: Grade specific treatment recommendations for imiquimod-related dermatologic/ local inflammatory reactions:

Severity (CTCAE Grading)	Description	Intervention concerning imiquimod treatment	Specific intervention
Pain of skin			
Mild (Grade 1)	Mild pain	Continue same dose	Consider oral acetaminophen or ibuprofen
Moderate (Grade 2)	Moderate pain; limiting instrumental ADL	Continue same dose unless Grade 2 skin pain continues for ≥ 2 days (48 hours) in which case treatment must be interrupted until recovered to ≤ Grade 1 followed by dose reduction	
Severe (Grade 3)	Severe pain; limiting self care ADL	Dose interruption until recovered to ≤Grade 1 followed by dose reduction*	See Grade 2; plus: an infectious process should be ruled out with pelvic exam and cultures.
Pruritis			
Mild (Grade 1)	Mild or localized; topical intervention indicated	Continue same dose	Topical polidocanol cream. Consider oral antihistamines, e.g. diphenhydramine, dimethindene, cetirizine,

HIC#: 1603017415 Protocol version 11.0

			levocetirizine, desloratidine, fexofenadine or clemastine)
Moderate (Grade 2)	Intense or widespread; intermittent; skin changes from scratching (e.g., edema, papulation, excoriations, lichenification, oozing/crusts); oral intervention indicated; limiting instrumental ADL	Continue same dose unless Grade 2 skin pain continues for ≥ 2 days (48 hours) in which case treatment must be interrupted until recovered to \leq Grade 1 followed by dose reduction	See Grade 1 plus oral histamines; Consider topical steroids (e.g., topical hydrocortisone)

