15.2 Analysis Set Definitions

- **full analysis set**—all randomized subjects
- safety analysis set—all subjects who have received at least one dose of any study drug, and/or have had any assessments at baseline or later that could be associated with an AE; analyzed by treatment received
- ITT analysis set—all randomized subjects with valid baseline measurements; analyzed by treatment assigned
- modified ITT analysis set—all randomized subjects with valid baseline measurements, receiving at least one dose of any study drug, and have at least one valid post-baseline measurement of outcome; analyzed by treatment assigned

HIC#: 1603017415 Protocol version 11.0

- modified ITT completers analysis set—all randomized subjects who receive at least one dose of
 any study drug and have complete and valid post-baseline assessments of outcome; analyzed by
 treatment assigned
- **per protocol analysis set**—all randomized subjects who receive all doses of their assigned study drug, have complete and valid post-baseline assessments of outcome, and have no protocol deviations (e.g. dose modification, assessment outside of time window, non-compliance)

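### The per-protocol set excludes women whose imiquimod was reduced or interrupted as the protocol directs, and this dose-based exclusion can occur only in the active arms

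*Combined protocol and SAP*

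**What the plan says.** Section 15.2 defines the per-protocol set by three conditions. The first is dosing: "all randomized subjects who receive all doses of their assigned study drug". The second is complete and valid outcome assessment after baseline. The third is that subjects "have no protocol deviations (e.g. dose modification, assessment outside of time window, non-compliance"). It makes no exception for changes that the protocol itself calls for.

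The treatment sections call for such changes in several places:
- Section 6.2.1, for persistent side effects: "the dose of the study medication will be modified and participants will receive vaginal suppositories containing only 50% of the original imiquimod dose".
- Section 7.1.1: "Treatment related toxicities will be managed by treatment interruptions and possible dose reductions of imiquimod according to the schedule" set out in its tables.
- Section 7.2.2, Table 2, for Grade 2 skin pain lasting 48 hours or more: "treatment must be interrupted until recovered to ≤ Grade 1 followed by dose reduction". Similar entries cover pruritus, ulceration and edema, and Grade 3 reactions also lead to interruption followed by reduction.
- Section 6.2.1 (also 4.1.2 and 7.2.3.2): "Subjects will be instructed to suspend the application of vaginal suppositories during the first 3 days of their menses".

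Missed doses are described differently for the two imiquimod arms in 6.2.1. Both texts allow make-up on the following day. After that, the imiquimod-only text says: "Otherwise, the dose must be skipped and subjects should take the next scheduled dose at the usual time". The imiquimod + vaccine text instead encourages completion of the whole course and permits the dosing period to be lengthened.

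Controls are observed only. Sections 15.5 to 15.7 name modified ITT as the main analysis. They say that sensitivity analyses on the modified ITT completers set, the per-protocol set, or both may be given.

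**The concern.** A per-protocol set should contain the subjects who were treated as the protocol says. Here, following the toxicity rules is itself a reason for exclusion: 6.2.1 describes halving the dose as modifying it, and 15.2 lists dose modification as a deviation.

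The exclusion is also one-sided. A woman who would have reacted badly to imiquimod is removed if she was randomised to imiquimod and kept if she was randomised to observation. The retained active subjects are then a subgroup chosen by tolerance and compared with controls not chosen that way. If tolerance is related to regression, for instance because local inflammation accompanies the immune response, the comparison is biased. A result that differed from modified ITT could then not be read as the effect in women treated according to protocol, which is the purpose of such a set.

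**Working it through.** **1. Treatment rules against the set definition**

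| Event handled as the protocol directs | Source | Status under 15.2 |
|---|---|---|
| Dose halved for toxicity | 6.2.1; 7.1.1; Table 2 | Excluded: listed deviation |
| Interruption for toxicity | 7.1.1; Table 2 | Excluded by the all-doses condition if any dose is not recovered |
| Suspension in the first 3 days of menses | 4.1.2; 6.2.1; 7.2.3.2 | Unclear: excluded only if the dose is not moved, made up or added by extension, and if it counts as missed |

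The first row needs no assumption. Missed doses fall under the separate all-doses condition, not under the list of deviations.

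**2. Which arms are exposed**

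The dose-based conditions can remove a woman for on-treatment events only in the imiquimod arms. Out-of-window assessment and non-compliance can remove women in any arm. Read literally, the all-doses condition is either empty for controls, who have no assigned drug, or removes all of them. Section 15.2 does not say which.

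**3. The menses instruction**

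Doses due: 2×1 + 2×2 + 4×3 = 18 in weeks 1-8 and 8×3 = 24 in weeks 9-16. The total is 42, which equals the number dispensed (boxes of 18 and 24), with no spares.

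- *Flexible days.* Section 6.2.1 sets doses per week, not weekdays. A 3-day suspension leaves 7 - 3 = 4 days for at most 3 doses, so all 42 can be taken.
- *Fixed days (assumption: days 1, 3 and 5 of each week at three per week; regular cycle of L days; random phase).* Mean scheduled doses on suspended days = 42×3/L. A dose cannot be made up the next day if it falls on the first or second suspended day, so the mean not recoverable = 42×2/L. For L = 28 these are 4.5 and 3.0, and 24 of 28 cycle phases (86%) lose at least one dose. For L = 24 they are 5.25 and 3.5. For L = 32 they are 3.94 and 2.63. In both of these cases every phase loses at least one dose.
- *Extension*, which only the imiquimod + vaccine text permits, can recover those doses.

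The menses effect therefore ranges from none to most regularly cycling women, depending on conventions that the documents leave open.

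**4. Precision if active subjects are removed**

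Inputs from 15.5 and 15.8: control rate 0.28, difference 0.35 (active rate 0.28 + 0.35 = 0.63), 38 per arm, one-sided Fisher test at 0.025. Exact power is the sum of Bin(x; n1, 0.63) × Bin(y; 38, 0.28) over all outcomes whose hypergeometric upper tail is at most 0.025. With n1 = 38 this gives 0.8269, which matches the table in 15.8.

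Now remove a share of one active arm and no controls, leaving the response rates unchanged (shares assumed):

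| Share removed | n1 | Power |
|---|---|---|
| 10% | 34 | 0.7998 |
| 20% | 30 | 0.7765 |
| 30% | 27 | 0.7498 |
| 50% | 19 | 0.6449 |
| 70% | 11 | 0.4163 |

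**5. Bias from selection on tolerance**

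Suppose there is no treatment effect, so the true rate is 0.28 in every arm. Let a share q of an active arm be dose-modified and respond at r times the rate b of the rest. Then q·r·b + (1 - q)·b = 0.28, so the rate in the retained women is b = 0.28/(q·r + 1 - q).

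| q | r | b | b - 0.28 |
|---|---|---|---|
| 0.2 | 0.5 | 0.311 | +0.031 |
| 0.2 | 1.5 | 0.255 | -0.025 |
| 0.4 | 0.5 | 0.350 | +0.070 |
| 0.4 | 1.5 | 0.233 | -0.047 |

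With r = 1 there is no bias. The documents give neither q nor r.

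**The case against.** The strongest reply is that a strict full-exposure set is a legitimate choice beside others. The modified ITT completers set keeps women who were reduced or interrupted, provided that their outcomes are complete. Section 15.4 tabulates dose received and treatment modifications by group. The per-protocol analyses are optional, and no test, alpha or power figure depends on them. This stands as a limit on the weight of the point. It does not remove it: the set is labelled per protocol, classes protocol-directed care as deviation, and does so in the active arms only.

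A reader might go further and infer that menstruating women can hardly ever complete 42 doses, so that the set would be nearly empty. The documents do not support that. It needs fixed weekdays, which they do not set, and it ignores the extension permitted in the imiquimod + vaccine text. Section 7.2.3.3 also provides for postmenopausal women and hormonal contraceptive users, so regular cycles cannot be assumed for everyone.

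A reader might also infer that almost all controls would stay in. Visit-window and compliance deviations can remove controls as well, and the all-doses condition has no settled meaning for them.

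**Conclusion.** The point holds for protocol-directed dose reductions on the text alone, and for interruptions whenever doses are not recovered. Suspension during menses may add to it, but how far cannot be determined from the documents. The consequence is a per-protocol comparison that selects on tolerance in the active arms only.

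Its size and direction are unknown. The figures of +0.070 to -0.047 and the power losses rest on assumed modification shares and response ratios, so they show what is possible, not what to expect. It would be wrong to infer that the bias favours imiquimod, or that the primary conclusion is at risk: the modified ITT analysis does not use these conditions. This is a moderate point, worth correcting because the correction is small.

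The two missed-dose texts in 6.2.1 (skip versus extend) could also make the all-doses condition exclude different shares of the two imiquimod arms. They must be reconciled.

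**What to change.** Amend the per-protocol definition in 15.2:
- State that interruptions, reductions and suspensions made as the protocol directs are neither deviations nor missed doses. Limit dose modification, as a deviation, to changes made outside the protocol's rules.
- Replace the all-doses condition with an adherence criterion: suppositories used, from the counts in 7.3, divided by doses due after those allowances. Fix the threshold before database lock and use the same one in both imiquimod arms.
- State that controls, who have no assigned drug, qualify on visit-window and outcome-assessment criteria.
- Reconcile the two missed-dose texts in 6.2.1 first, because the denominator of doses due depends on them.

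The cost is SAP wording plus that reconciliation. Diaries and suppository counts are already collected. The downside is a set slightly less strict on exposure.

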15.3 Subject Disposition

Using a flowchart with counts and percentages, a breakdown of the study dispositions for **all screened subjects** will be provided. 'Disposition' refers to eligibility, consent, enrollment, randomization assignment, dosing, drop-out prior to completion of full protocol, completion of protocol, follow-up. Reasons for drop-out will also be summarized.

15.4 Demographics, clinical measures, and safety

Summary statistics will be used to describe demographics and clinical measures collected at **baseline** using **ITT analysis set**, and will be presented by assigned treatment group and overall. Baseline characteristics will be tested for homogeneity across treatment arms using a 2-sided Fisher's Exact Test for categorical measures and ANOVA or Wicoxon Rank-Sum Test for continuous variables. Standard tables and listings will be provided for ongoing assessments, including (but not limited to) study drug dose received, treatment modifications, concomitant medications, labs, vital signs, and clinical tests, and will be reported by subject, by time point, and by treatment group, as appropriate. AEs/SAEs will be reported by subject, by time point, and by treatment group, using the **safety analysis set**.

15.5 Analysis for the Primary Objective

The co-primary objectives of this study are to test superior treatment efficacy of Imiquimod + HPV vaccine (Trt1) compared to control (Trt0), and likewise Imiquimod only (Trt2) compared to control (Trt0). The primary outcome is *histologic regression* (yes/no) after completion of the 12 to 16 weeks imiquimod course. The full definition of *histologic regression* and how it is determined is described in Section 5.1.

The co-primary hypothesis tests are:

 $\{H_{01}: p_1 - p_0 = 0 \text{ versus } H_{11}: p_1 - p_0 > 0\}$ and

 $\{H_{02}: p_2 - p_0 = 0 \text{ versus } H_{12}: p_2 - p_0 > 0\}$

 p_0 , p_1 , and p_2 are the proportion of subjects on Trt0, Trt1, and Trt2, respectively, who are determined to have *histologically regressed*. Fisher's Exact Test will be used to assess if the data support rejecting the null hypothesis H_{01} , and likewise for H_{02} . To control Type I error, we will use a conservative Bonferroni adjustment for multiple comparisons with one-sided $\alpha = (0.05)/2 = 0.025$ as the significance level for each test. Rejection of a particular null hypothesis suggests superior efficacy of that specific treatment compared to control. Exact 95% confidence intervals will be calculated for p_1 - p_0 and for p_2 - p_0 . Confidence intervals for 'risk ratios' (p_1/p_0 , p_2/p_0) in addition to 'risk differences' (p_1 - p_0 , p_2 - p_0) may also be estimated. The main analysis will use the **modified ITT analysis set**. Sensitivity analyses for the same statistical method using the **modified ITT completers** and/or **per protocol analysis sets** may also be provided.

HIC#: 1603017415 Protocol version 11.0

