15.1 General Statistical Considerations

- Type I error for hypothesis testing will be $\alpha = 0.05$, and 95% confidence intervals will be used for parameter estimation, unless otherwise specified. Type II error will be based on $\beta = 0.10$, unless otherwise specified. Only the primary analysis will use an adjustment for multiple comparisons.
- Summary statistics for continuous variables will include (but may not be limited to) the number of observations, mean, standard deviation, minimum, median and maximum. For categorical variables, summary statistics will include (but may not be limited to) counts, percentages, and cross-tabulation tables.
- Standard diagnostics will be performed to assess whether the assumptions for specific parametric statistical methods are adequately supported by the data. Should parametric methods be inappropriate, the analogous non-parametric methods will be used and only these results will be reported.
- Imputation of missing values will not be applied.
- No interim analyses for efficacy or futility are planned, although the trial may be stopped early based on observations from continual safety monitoring.
- Data analysis will be conducted using SAS® v9.4 (or later).

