15.8 Sample Size Justification

Anticipated annual accrual is approximately 40-45 subjects.

Our general philosophy regarding Phase II trials of new drug combinations is to facilitate the prompt discovery of inactive agents, yet allow for a reasonable estimate of the response rates for those regimens demonstrating some degree of activity. However, excessive accrual to inactive study regimens to document precise response rates is to be avoided. The purpose of this study is to evaluate the activity and potential toxicity of the combination therapy of Imiquimod + HPV vaccine in subjects with untreated high-grade CIN 2,3 cervical dysplasia. This study will implement a 3 arm randomized trial design that will allow us to estimate the treatment effect of Imiquimod + HPV vaccine compared to observation as well as Imiquimod alone compared to observation.

Based on published literature for the primary outcome,³⁸ we assume a 28% spontaneous histological regression rate in CIN 2-3 lesions with observation alone (control group). From Grimm et al.'s efficacy

HIC#: 1603017415 Protocol version 11.0

trial of imiquimod for treatment of CIN 2-3, we would like to have sufficient power to detect a 35% absolute increase in rate of histologic regression in the imiquimod only arm compared to control. Based on this data, we consider a conservative effect size estimate also of an absolute 35% higher rate of histologic regression in the imiquimod + HPV vaccine intervention arm compared with the control arm. We therefore aim to recruit a total sample size of 114 subjects (38 in each arm). Calculations based on Fisher's Exact Test indicate we will have $\geq 90\%$ power to detect a treatment effect of $\geq 29\%$ in both treatment arms independently compared to the observation arm ($\alpha = 0.025$ for each comparison to control). In addition, with n = 38 subjects per arm, we would have 80% power to detect a treatment effect size of $\geq 25\%$ in one treatment arm compared to placebo (while maintaining 90% power to detect the treatment effect size of $\geq 25\%$ in the other arm). Assuming a subject dropout rate of 20%, a total sample size of 138 (n = 46 per arm) subjects is calculated which will be recruited over 5 years.

Some operating characteristics of the study design are as follows:

Exact Operating Characteristics for the Treatment Effect Size Δ given control group rate=0.28, n=38 subjects per arm, one-sided α

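### Fisher's exact test leaves part of the allotted one-sided 0.025 unused; Boschloo's unconditional exact test would recover about 0.3 to 6 points of power near the planned arm sizes, with no added patients

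*Combined protocol and SAP*

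**What the plan says.** Section 15.5 sets two one-sided hypotheses, each active arm superior to control. It tests each with Fisher's test: "Exact Test will be used to assess if the data support rejecting the null hypothesis". A Bonferroni split of 0.05 gives one-sided 0.025 "as the significance level for each test". The section also promises exact 95% confidence intervals for the two risk differences, without naming a method.

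Section 15.8 gives the design assumptions. For control, "we assume a 28% spontaneous histological regression rate in CIN 2-3 lesions with observation alone (control group". The effect sought is to "detect a 35% absolute increase in rate of histologic regression in the imiquimod only arm compared to control", and the same 35 points is used for the combination arm. On numbers: "We therefore aim to recruit a total sample size of 114 subjects (38 in each arm"), then "Assuming a subject dropout rate of 20%, a total sample size of 138 (n = 46 per arm) subjects is calculated". Section 15.1 sets the default type II error at 0.10.

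The operating-characteristics table in 15.8 reports, for a nominal 0.025 and 38 per arm, an actual alpha between 0.0140 and 0.0149 across its columns. It gives a power of 0.8269 at a 35-point difference. The prose above the table claims at least 90% power at 29 points. No unconditional exact test is mentioned, and no reason is given for preferring a conditional one.

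**The concern.** Fisher's test conditions on the total number of responders. Its p-value can then take only a few values near 0.025, and the true type I error falls well short of the level allowed. At 38 per arm it uses at most 0.0149 / 0.025 = 60% of the allowance, after Bonferroni has already halved the overall 0.05. The unused part is lost power on the primary endpoint.

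An unconditional exact test on the two independent binomials also guarantees the level and gives up less of it. The trial is short of its 90% target at the 35-point design effect, and recruitment is planned over five years. Power that needs no extra patients is therefore worth having.

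**Working it through.** **Inputs.** Control rate 0.28, difference 0.35 (so 0.63 on treatment), 38 per arm evaluable and 46 per arm enrolled, all from 15.8. One-sided 0.025 and Fisher's test from 15.5. Target power 0.90 from 15.1.

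**Formulas.** Let x1 and x0 be the responders among n1 treated and n0 control subjects, with s = x1 + x0.

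- Fisher p(x1, x0) = sum over k ≥ x1 of C(n1,k)·C(n0,s−k) / C(n1+n0,s). Reject if p ≤ 0.025.
- Power = sum of b(x1; n1, 0.63)·b(x0; n0, 0.28) over all rejecting outcomes, where b is the binomial probability.
- Size at a common rate π is the same sum with both rates equal to π. Maximum size is taken over 1,999 values of π from 0.0005 to 0.9995.
- Boschloo: reject if Fisher p ≤ c, where c is the largest cut-off with maximum size ≤ 0.025. At 46 per arm, for example, c = 0.0376. The cut-off 0.025 itself always meets the size condition, so c is never below 0.025 and every Fisher rejection is kept.

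**Step 1: reproduce the plan.** Enumerating all 39 × 39 outcomes at 38 per arm gives Fisher power of 0.6860, 0.7472, 0.8269, 0.8706 and 0.9215 at differences of 0.30, 0.32, 0.35, 0.37 and 0.40. All five match the table to four decimals. Size is 0.0147 at a common rate of 0.28, as in the table's zero-difference column, and at most 0.0149 at any common rate.

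**Step 2: change only the test.** Power for 0.28 versus 0.63:

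| Evaluable, treatment/control | Fisher max size | Fisher power | Boschloo max size | Boschloo power | Gain (points) |
|---|---|---|---|---|---|
| 36/36 | 0.0139 | 0.7885 | 0.0247 | 0.8516 | 6.3 |
| 37/37 | 0.0144 | 0.8084 | 0.0237 | 0.8661 | 5.8 |
| 37/38 | 0.0186 | 0.849 | 0.0242 | 0.853 | 0.3 |
| 38/37 | 0.0186 | 0.8439 | 0.0242 | 0.8603 | 1.6 |
| 38/38 | 0.0149 | 0.8269 | 0.0222 | 0.8665 | 4.0 |
| 40/40 | 0.0165 | 0.8595 | 0.0238 | 0.8836 | 2.4 |
| 42/42 | 0.0188 | 0.8872 | 0.0241 | 0.8946 | 0.7 |
| 44/44 | 0.0153 | 0.8746 | 0.0239 | 0.9113 | 3.7 |
| 46/46 | 0.0151 | 0.8948 | 0.0235 | 0.9285 | 3.4 |

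Fisher's power follows a sawtooth: 42 per arm does better than 44. The gain moves with it.

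**Step 3: where the trial is likely to land.** On the plan's own 20% dropout, 46 × 0.8 = 36.8, or about 37 per arm. At 37/37 the change is 0.8084 to 0.8661, but an imbalance of one subject changes the gain a good deal.

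**Step 4: the stated power.** At 38 per arm and 29 points, Fisher gives 0.6535 and Boschloo 0.720. Neither is near 0.90. At 35 points neither reaches 0.90. Boschloo first passes it in the 37-point column (0.9012), Fisher in the 40-point column (0.9215).

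**The case against.** The strongest reply is that nothing here is wrong. Fisher's test controls type I error, is prespecified and is familiar, and some statisticians prefer conditional inference for a two-by-two table. The plan also tabulates both the actual alpha and the resulting power, so the conservatism is disclosed. All of that stands, and it is why this is a matter of efficiency. It does not remove the gain: no reason is given for accepting the loss, and the prose claim of 90% at 29 points does not agree with the table that discloses it.

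A second reply is that exactly 38/38 is unlikely and the benefit can be slight. This also stands. A reader might take four points as a fixed gain, or 0.015 as a fixed size. The documents do not support either, because the primary set is whoever is evaluable under modified ITT. At 37/38 Fisher's maximum size is 0.0186 and the gain is 0.3 points.

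A reader might also infer that changing the test delivers the planned 90%. At 38 per arm it does not. Adding a Holm procedure to Boschloo's test would bring per-comparison power to 90.3%, but only if both active arms truly have the 35-point effect. If the other arm is at the control rate, power stays at 86.7%. Holm is a separate change and is not part of this point.

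**Conclusion.** The point holds as a cheap improvement. At the planned 38 per arm, Fisher's test uses at most 0.0149 of 0.025 and gives 82.7% power for 28% versus 63%. Boschloo's test uses up to 0.0222 and gives 86.7% with the same patients. For evaluable sizes near the plan the gain at 35 points is about 0.3 to 6 points, and it was never negative in the cases checked.

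These figures assume independent binomial outcomes with the evaluable arm sizes taken as fixed, a 28% control rate, and a one-sided 0.025 per comparison. The claim of at least 90% power at 29 points is a separate and larger defect, which a change of test does not cure.

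**What to change.** - **15.5:** name Boschloo's one-sided unconditional exact test at 0.025 as the single primary test for H01 and H02, with the cut-off computed from the evaluable arm sizes. Report Fisher's p-value alongside.
- **15.5, intervals:** specify an exact unconditional 95% interval for each risk difference that is consistent with the test, so that its lower limit and the test decision cannot disagree.
- **15.8:** restate power for the chosen test. With Boschloo at 38 per arm that is 86.7% at 35 points and 72.0% at 29 points; if Fisher's test is kept, 82.7% and about 65%. The 25-point, 80% sentence must go too: the table's Fisher power is only 0.6860 at 30 points, so it is lower still at 25.
- **Timing:** make the change before any outcome data by arm are seen. If that moment has passed, keep Fisher's test as primary and report Boschloo's as a sensitivity analysis.

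The cost is an amendment through the IRB (Section 14.6), a short program, and a test that some readers will know less well. No patients or visits are added.
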